### **7.3 Study Drug Packaging and Labeling**

GC4419 will be presented as individual single-use vials, which represent daily doses to be administered IV concurrent with SBRT. Details regarding labeling can be found within the Pharmacy Manual.

### **7.4 GC4419**

GC4419 is packaged as an 11 mL  $\pm$  0.1 mL aliquot in a 10 mL amber glass vial with a S-127 4432/50 gray stopper and a 20 mm red flip-off seal. Each bottle will be labeled with the appropriate language, including the required regulatory text.

### **7.5 Placebo**

Placebo vials will not be provided by the Sponsor. The Site will be responsible for preparing placebo IV infusion bags with 250 mL of 100% normal saline per the Pharmacy Manual.

### **7.6 Study Drug Storage**

GC4419 solutions must be stored at 2°C to 8°C at all times until use. GC4419 solutions must not be frozen at any time. Temperature excursions above freezing and up to 25°C or down to 0.1°C for four hours are acceptable; however, Galera Therapeutics, Inc. or its designee must be notified immediately of the temperature excursion to ensure proper oversight.

Once prepared, the IV bags containing GC4419/saline mixtures must also be stored at 2°C to 8°C until use, and must be administered to patients within 24 hours of preparation. GC4419 dosing solutions must not be frozen at any time. If freezing of the material is evident, that supply must be quarantined per institutional guidelines and Galera Therapeutics, Inc. or its designee must be notified immediately.

### **7.7 Study Drug Preparation GC4419 and Placebo**

GC4419 will be provided to the study site in single use, sterile, pyrogen-free vials ready for dose preparation. Proper mixing with normal saline is required. Standard aseptic techniques will be used to maintain sterility.

Assignment of treatment arm will be randomized with respect to treatment arms A (90mg GC4419) and B (placebo). GC4419 will be presented in single-use vials.

To prepare daily IV solutions of GC4419, investigational pharmacists will extract 10 mL from a single vial and add to 240 mL normal saline. Note that there is no extraction of saline (i.e., the infusion solution volume will be 240 mL saline + 10 mL volume of GC4419/placebo). No additional modifications or adjustments are to be made to the infusion solution.

The GC4419 solution may appear clear or have a slight yellowish tint. Although solutions should be free of particulates, it is possible that some vials may have some fine visible particulates. Infusions should be prepared using a sterile 0.2 micron syringe filter prior to introduction into the infusion bag. The prepared admixture should be inspected visually for any particulate matter prior to administration, and prepared solutions still containing any visible particles after filtration should not be used. Filtration does not influence dosage calculations.

To prepare daily IV solutions of placebo, investigational pharmacists will use 250 mL of 100% normal saline.

Further information and preparation details will be provided in a separate Pharmacy Manual.

Note: Investigational staff who prepare infusion solutions will be unblinded and cannot be discussed with the clinical team.

## 7.8 Study Drug Administration

**GC4419 and Placebo:** GC4419 or Placebo/saline mixture will be administered intravenously at an infusion rate that totals 60 min ( $\pm$  6 min to account for saline overfill) for the total dose assigned. Infusions of GC4419/placebo must be administered using an infusion pump (i.e., not by drip rate). Infusion pump models are not specified and may be per institutional preference/standard.

To facilitate administration of GC4419 according to the study schedule, an indwelling venous access device may be used, at the discretion of the treating investigator. If an indwelling venous access device is placed to facilitate administration of GC4419, this fact will be recorded with the study data, as will information about the date of placement, type of device, and subsequent complications or adverse events related to the use of the device.

SBRT must be initiated as soon as possible upon completion of the GC4419/placebo infusion, but no later than 180 minutes following the end of the GC4419/placebo infusion.

GC4419/placebo will be given beginning on the first day of radiation and continuing daily, concurrently M-F throughout the administration of SBRT

If SBRT is not administered on any given day due to a treatment break or unforeseen circumstances, GC4419/placebo should not be administered on that day. Breaks in SBRT will be determined by the patient's treating physician in accordance with standard of care. Patients should resume GC4419/placebo administration when SBRT resumes. On days when planned doses of both GC4419/placebo and SBRT are not administered (e.g., due to a holiday site closure), GC4419/placebo dosing may be extended along with SBRT to make up the missed dose(s).

## 7.9 Study Drug Accountability

The investigator is responsible for ensuring adequate accountability of all used and unused GC4419. This includes acknowledgment of receipt of each shipment of GC4419 (quantity and condition), patient dispensing records, and quantity of GC4419/placebo returned or destroyed. Dispensing records will document quantities received from Galera Therapeutics, Inc. and quantities dispensed to patients, including container number or lot number, date dispensed, patient identifier number, patient initials, and the initials of the person dispensing the medication. Any GC4419 that is prepared but not used must also be recorded in the dispensing records. Further accountability instructions can be found in the Pharmacy Manual.

All GC4419 supplies and associated documentation will be reviewed and verified by the study monitor. Copies of all forms, documenting drug receipt at the study site, drug transportation to satellite sites, and drug return to Galera Therapeutics, Inc., together with drug accountability records, will be retained according to the regulations governing record retention.

The investigator will not allow GC4419/placebo to be given to any patient not included in the study or any unauthorized person.

## 7.10 Study Drug Handling and Disposal

**GC4419:** After completion of the study, all unused study drug will be inventoried by the study monitor and if possible, destroyed locally at the site after complete accountability by the Sponsor and/or its representatives. GC4419 should not be returned directly to Galera Therapeutics, Inc. unless specifically requested by Galera Therapeutics, Inc. The study monitor will instruct the site in the disposal and/or destruction of all used and unused GC4419 supplies. Destruction of any GC4419 should be documented appropriately.

## 8.0 DOSE AND TREATMENT MODIFICATIONS

### 8.1 Ancillary therapy, concomitant medications and supportive care

Necessary supportive measures for optimal medical care will be given throughout the study. Supportive care medications may be administered at the investigator's discretion and recorded in the CRF (including administration of prophylactic antiemetic and antidiarrheal medication if deemed appropriate by the investigator). Concomitant medications will be recorded in the eCRF up to Week 12 for AEs and until resolution of SAEs. However, medications are subject to the following exclusions:

- Other concurrent chemotherapy or investigational agent during the week of SBRT
- Nitrates, phosphodiesterase type 5 (PDE 5) inhibitors (e.g., sildanefil, tadalafil, or similar agents) or other drugs that in the judgment of the treating investigator could create a risk of a precipitous decrease in blood pressure are prohibited until at least 24 hours after the last dose of GC4419
- Pyridostigmine or other drugs that in the judgment of the treating investigator could create a risk of increased carotid sinus sensitivity, symptomatic bradycardia, or syncopal episodes.
- Other biologic response modifiers – except systemic hematopoietic growth factors for the management of anemia or myelosuppression
- Concurrent approved or investigational anti-cancer therapy (e.g., chemotherapy, immunotherapy, targeted therapy, hormone and biologic therapy) other than the Protocol regimen
- Other investigational agents

### 8.2 Dose Delays and Dose Modifications

The following toxicities require a 25% dose reduction in GC4419/placebo:

- Grade 2 or greater hypotension within two hours after the start of GC4419/placebo infusion
- Grade 3 or 4 vomiting, or Grade 3 nausea

Two dose reductions for toxicity will be permitted per patient. After the first event, the patient will be re-challenged at 75% of the original dose (7.5 mL GC4419/placebo in normal saline for a total volume of 250 mL). After the second event, the patient will be re-challenged at 50% of the original dose (5.0 mL GC4419/placebo in normal saline for a total volume of 250 mL). Patients who are unable to tolerate GC4419/placebo infusions following two dose reductions must be discontinued from the study treatment but may continue with SBRT at the discretion of the treating investigator.

For other toxicities (including those attributable to SBRT), management will be per institutional and ASCO guidelines and investigator judgment.

Any radiation related toxicities  $\geq$  grade 4 will necessitate removal of patient from further SBRT.

## 9.0 ADVERSE EVENTS

### 9.1 Definitions

The treating physician and investigator team are responsible for the detection and documentation of events meeting the criteria and definition of an adverse event (AE) or serious adverse event (SAE) as provided in this protocol. Throughout the study, AEs will be recorded in the source documents and on the appropriate pages of the CRF regardless of whether the AEs are considered related to GC4419/placebo, SBRT or other cause. To avoid confusion, the AE should be recorded in standard medical terminology.

The following definitions of terms are guided by the International Conference on Harmonization and the US Code of Federal Regulations and are included here verbatim.

#### **Adverse Event (AE):**

An AE is any untoward medical occurrence in a patient or clinical investigation subject administered a pharmaceutical product and which may or may not have a causal relationship with this treatment. An AE can therefore be any unfavorable and unintended sign (including an abnormal laboratory finding), symptom, or disease temporally associated with the use of a medicinal (investigational) product, whether or not related to the medicinal (investigational) product.

Examples of an AE include:

- Significant or unexpected worsening or exacerbation of the condition/indication under study.
- Exacerbation of a chronic or intermittent pre-existing condition including either an increase in frequency and/or intensity (grade) of the condition.
- New conditions detected or diagnosed after investigational product administration even though they may have been present prior to the start of the study.
- Signs, symptoms, or the clinical sequelae associated with a suspected interaction of the investigational product with a concomitant medication.
- Signs, symptoms, or the clinical sequelae associated with a suspected overdose of either investigational product or a concurrent medication.

#### **Serious Adverse Event (SAE):**

Any untoward medical occurrence that at any dose:

- Results in death,
- Is life-threatening – NOTE: The term ‘life-threatening’ in the definition of ‘serious’ refers to any adverse drug experience [adverse event] that places the patient or subject, in the view of the investigator, at immediate risk of death from the reaction as it occurred, i.e., it does not include a reaction that, had it occurred in a more severe form, might have caused death. [emphasis added]
- Requires inpatient hospitalization or prolongation of hospitalization – NOTE: In general, hospitalization signifies that the patient or subject has been detained (usually involving at least an overnight stay) at the hospital or emergency ward for observation and/or treatment that would not have been appropriate in the physician’s office or outpatient setting. Complications that

occur during hospitalization are AEs. If a complication prolongs hospitalization or fulfills any other serious criteria, the event is serious. When in doubt as to whether “hospitalization” occurred or was necessary, the AE should be considered serious. Hospitalization for elective treatment of a pre-existing condition that did not worsen from baseline is not considered an AE.

- Results in persistent or significant disability/incapacity – NOTE: The term disability means a substantial disruption of a person’s ability to conduct normal life functions.

OR

- Is a congenital abnormality/birth defect.
- Other Important Medical Event

## 9.2 Serious Adverse Event Reporting

All events meeting the criteria for Serious Adverse Events (listed in [section 9.1](#)) must be reported to the Sponsor by investigational sites within 24-hours of becoming aware of the event. In order to determine the sponsor’s timeline for notifying regulatory authorities and investigators per Federal Regulations, an event term, serious criteria, and causality is required at the time of the initial report. Specific SAE reporting instructions are provided in a separate manual.

The investigator will also notify your local IRB in writing of serious events per the IRB reporting policy.

## 9.3 Routine Adverse Event Reporting

Any adverse medical condition or laboratory abnormality with an onset date before the date of randomization is considered to be pre-existing in nature, and part of a patient’s medical history. Adverse medical conditions that begin on or after date of randomization will be considered an adverse event. Increases in toxicity grade of pre-existing conditions that occur on or after the date of randomization are also considered an adverse event. AEs and SAEs occurring up to 1 year after SBRT will be recorded in the electronic data capture system. All SAEs will be followed to resolution; i.e., until they no longer meet criteria for seriousness. Non-serious AEs will be followed to resolution to the extent possible for up to one year post-SBRT. The frequency of routine AE assessments will be as indicated in the schedule of events.

All adverse events must be recorded in the patient’s source documents and on the CRF regardless of frequency, severity (grade) or assessed relationship to randomized therapy.

Gastrointestinal toxicity will be carefully assessed for causality because GI toxicity will be used in the primary endpoint. Disease progression or death due to disease progression will not be reported as an AE as it is captured as a study endpoint in the CRF. Progressive disease found by scan or on clinical evaluation should be captured on the applicable CRF pages and not on the AE page.

## 9.4 Grading and Cause Assignment of Adverse Events

The severity of adverse events will be designated as mild, moderate, severe, life threatening, or fatal per NCI CTCAE version 4.03. If not specifically addressed in NCI CTCAE version 4.03, use [table 3](#) below. Cause assignment of adverse events will be made in accordance

with table 4 below. The Investigator should consult the Investigator Brochure and/or product information in the determination of his/her assessment.

Table 3. Grading of Adverse Events

| Grade                      | Criteria   |
|----------------------------|--|
| Mild – Grade 1             | Asymptomatic or mild symptoms; clinical or diagnostic observations only; intervention not indicated  |
| Moderate – Grade 2         | Minimal, local, or noninvasive intervention indicated; limiting age-appropriate instrumental ADL   |
| Severe – Grade 3           | Severe or medically significant but not immediately life-threatening; hospitalization or prolongation of hospitalization indicated; disabling; limiting self-care ADL  |
| Life Threatening – Grade 4 | Life-threatening consequences; urgent intervention indicated   |
| Death – Grade 5            | Death related to adverse event   |

Table 4. Cause Attribution of AE's

| Attribution             | Definition   |
|-------------------------|--|
| Related          | It is likely that GC4419/placebo caused or contributed to the cause of the adverse event or laboratory abnormality, when the temporal sequence from the time of GC4419/placebo or SBRT administration, the known consequences of the patient's clinical/state condition or study procedures, the effects of discontinuing or reintroducing GC4419/placebo on the adverse event, and other medically relevant factors are considered.               |
| Possibly Related | There is a reasonable possibility that the adverse event or laboratory abnormality was caused by GC4419/placebo or SBRT, when the temporal sequence from the time of GC4419/placebo administration, the known consequences of the patient's clinical state/condition or study procedures, and other medically relevant factors are considered.   |
| Unrelated        | The investigator has a high level of certainty that the patient's clinical state/condition, study procedures, or other medically relevant factors other than treatment with GC4419/placebo or SBRT caused the adverse event or laboratory abnormality. This relationship category should only be used when a clear precipitating cause exists and it is not reasonably possible that the event is caused by treatment with GC4419/placebo or SBRT. |

## 10.0 ASSESSMENTS

### 10.1 Schedule of Evaluations

See Study Calendar in [section 5.0](#).

### 10.2 Safety Assessments

General safety will be assessed during radiation, weekly (see visits on the basis of treatment-emergent AEs, physical examination findings, clinical laboratory tests, and vital sign measurements).

### 10.3 Clinical Assessments

Clinical assessment will consist of standard history and physical examination by a physician, nurse-practitioner or physician assistant responsible for the oncologic care of the patient.

Long-term follow-up may include telephone calls by study staff where clinic follow up is not feasible.

### 10.4 Laboratory Assessments

All protocol required laboratory assessments in the study calendar [section 5.0](#) will be performed at a local laboratory.

### 10.5 Endoscopic Assessment

The endoscopic evaluation (including EUS) will take place at approximately 12 weeks post radiation. The endoscopist will be blinded to receipt of drug versus placebo. The following scale will be used for assessment where a score of 0=no toxicity, 1-2 indicates mild toxicity, 3-4 indicates moderate toxicity and 5 or more indicates severe toxicity:

- Erythema: (0=none, 1=mild (looks pink), 2=moderate/severe (red))
- Edema: (0=none, 1=mild, 2=moderate/severe)
- Ulcers: (0= none, 1= single, 2= 2 or more ulcers)
  - If ulcers are present, the endoscopist will measure cumulative surface area to normalize for ulcer size.
  - Note will also be made of whether ulcer has a clean base, active bleeding or stigmata of recent bleeding
- Stricture: (0-none 1= mild, 2=moderate/severe)

The endoscopist will also record the location of the tumor using anatomic coordinates including stomach (antrum, lesser and greater curvature, anterior and posterior wall) and duodenal bulb (medial or lateral wall), second portion of the duodenum (medial or lateral wall).

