## 4.0 PATIENT SELECTION

### 4.1 Inclusion Criteria

1. Cytologic or biopsy confirmed adenocarcinoma of the pancreatic head, body or tail
2. Disease that is appropriate for SBRT by virtue of being:
  - a. Locally advanced and technically unresectable, as determined by a pancreaticobiliary surgeon as part of a multidisciplinary review at the investigative site, including multi-phasic CT demonstrating:
    - i. Greater than 180 degree tumor involvement of the superior mesenteric artery
    - ii. Greater than 180 degree tumor involvement of the celiac axis, including major branches of the celiac axis that render it unresectable (e.g. common hepatic artery).
    - iii. Tumor involvement of the first branch of the SMA that is not surgically reconstructible
    - iv. Long segment involvement of the superior mesenteric vein/portal vein or hepatic artery that is not surgically reconstructible
  - b. Potentially resectable, but patient is judged not a candidate for surgery, after multidisciplinary review at the investigative site;
  - c. Potentially resectable, but the patients refuses surgery and is considered an acceptable candidate for SBRT after multidisciplinary review at the investigative site;
  - d. "Borderline" resectable, as determined by multidisciplinary review, including absence of distant lymphadenopathy and the primary tumor characterized by one of more of the following:
    - i. A tumor-vessel interface (TVI) with the mesenteric vein (SMV) or portal vein (PV) measuring  $\geq 180^\circ$  of the circumference of either vein's wall or short-segment occlusion of either vein with a normal vein above or below the obstruction amenable to reconstruction;
    - ii. Any TVI with the common hepatic artery (CHA) with normal artery proximal and distal to the TVI amenable to reconstruction;
    - iii. A TVI with the superior mesenteric artery (SMA) measuring  $< 180^\circ$  of the circumference of the vessel wall
3. Primary tumor size and limited bowel involvement by tumor must be judged acceptable for SBRT at the discretion of the treating investigator.
4. No evidence of distant metastasis either prior to or after induction chemotherapy.
5. Completion of medically indicated first-line chemotherapy, as determined by the treating investigator
6. Patient must have metal stent in place if duodenal stent is required. If patient has plastic stent, this must be replaced prior to radiation.

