#### **4.2 Exclusion Criteria:**

1. Prior radiation therapy to the abdomen that would overlap with treatment field
2. Prior surgical resection of pancreatic tumor
3. Receiving any approved or investigational anti-cancer agent other than those provided for in this study
4. Uncontrolled or active gastric or duodenal ulcer disease within 30 days of dosing
5. Visible invasion of tumor into the lumen of the bowel or stomach on endoscopy (Note: Radiological infiltration into bowel is allowed, unless deemed clinically unsafe.)
6. Residual or ongoing  $\geq$  Grade 3 non-hematologic toxicity from chemotherapy
7. Contraindication to IV contrast
8. Concurrent participation in another interventional clinical trial or use of another investigational agent within 30 days of study consent Note: Patients who are participating in non-interventional clinical trials (e.g., QOL, imaging, observational, follow-up studies, etc.) are eligible, regardless of the timing of participation.
9. Uncontrolled intercurrent illness including, but not limited to, ongoing or active infection, symptomatic congestive heart failure, unstable angina pectoris, renal failure, cardiac arrhythmia, or psychiatric illness that would limit compliance with treatment
10. Second primary malignancy within the last 5 years, unless treated definitively and with low risk of recurrence in the judgment of the treating investigator
11. Known history of HIV or active hepatitis B/C (patients who have been vaccinated for hepatitis B and do not have a history of infection are eligible)

12. Female patients who are pregnant or breastfeeding
13. Women of child-bearing potential who are unwilling or unable to use an acceptable method of birth control to avoid pregnancy for the entire study period and for 30 days after the last dose of GC4419. Acceptable methods include, but are not limited to, barrier methods, IUD, and birth control pills. This includes any woman who has experienced menarche but has not undergone successful surgical sterilization or is not postmenopausal (defined as amenorrhea for at least 12 consecutive months, or women on hormone replacement therapy with serum FSH levels greater than 35 mIU/mL). A negative urine or serum pregnancy test must be obtained within 14 days prior to the start of study therapy in all women of child-bearing potential.

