| Adverse Event Assessment†   |   | X (1)                   | X (1)                   | X (1)   | X (1)                                | X (1)                                 | X (1)                      |
| PRO-CTCAE   | X (2)                                     | X(2)                    | X                       | X   | X                                    | X                                     | X                          |
| Fatigue/QOL/Physical/Mental LASA Assessment   | X (2)                                     | X(2)                    | X                       | X   | X                                    | X                                     | X                          |
| Endoscopy with Fiducial placement for CT guided on-line positioning (not necessary for MR-linac treatments), core biopsies, cytologic brushings | X*  |                         |                         |   |                                      |                                       |                            |
| Endoscopy with duodenal evaluation, core biopsies if possible, cytologic brushings  |   |                         |                         |   |                                      | X (5)                                 |                            |

|  |       |       |       |       |       |       |       |
|--|-------|-------|-------|-------|-------|-------|-------|
| Radiation Simulation (>5 business days prior to SBRT and following eligibility)***         | X     |       |       |       |       |       |       |
| Laboratory Studies  |       |       |       |       |       |       |       |
| Electrocardiogram (ECG)  | X     |       |       |       |       |       |       |
| CBC, Differential, Platelets   | X     | X     | X     | X     | X     | X     | X     |
| Chemistry (Serum Creatinine, Electrolytes, AST, ALT, Alk. Phos., Albumin, Total Bilirubin) | X     | X     | X     | X     | X     | X     | X     |
| Pregnancy Test (#)   | X     |       |       |       |       |       |       |
| Tumor marker (CA 19-9)   | A     | A     | A     | A     | A     | A     | X     |
| Blood and Tissue Collection for Correlatives   |       | X (4) | X (4) | X (4) | X (4) | X (4) | X (4) |
| Evaluation for Resectability (7)   | X     |       |       |       | X     |       |       |
| Staging   |       |       |       |       |       |       |       |

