## 6.0 RADIATION DELIVERY

### 6.1 Radiotherapy Technical Factors

#### 6.1.1 Eligibility criteria for SBRT

In order to ensure safety, patients must meet the following criteria in order to proceed with SBRT:

- Patients must have no evidence of active duodenal or gastric ulcers or direct tumor invasion of the bowel or stomach on pre-SBRT endoscopy. Previous history of ulcers >30 days prior to treatment with no active bleeding or symptoms are eligible for treatment.
- Patients should not be treated with SBRT if SBRT-specific organ at risk (OAR) constraints (listed in [section 6.3](#)) cannot be met.
- Patients must be able to undergo 4D CT simulation to assess tumor motion with respiration and able to comply with breath hold for motion management.
- Patient must not have any contraindication to contrast administration at simulation, including contrast allergy refractory to premedication at the discretion of the treating physician.
- Patient must have a functioning metal stent in place if biliary or duodenal stent is required.

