### 12.9.2 Secondary Endpoints and Analysis

Secondary outcomes will include progression-free survival (PFS) time and overall response rate in addition to rate of long-term toxicity, surgical resection and rates of R0 and pathologic complete response at resection. Unadjusted distributions of the time-to-event outcomes PFS and OS will be estimated using the method of Kaplan and Meier and their relationship to prognostic covariates and RT cell dose level will be evaluated by Bayesian piecewise exponential survival regression.

Resectability will be assessed at the seven week time point. If a patient goes on to resection, he or she will be categorized as acceptable efficacy. If the patient is deemed unresectable, efficacy will be reassessed at 12 weeks. Toxicity will also be assessed at the 12 week timepoint and descriptive statistics will be generated. If endoscopy exhibits severe toxicity, the patient will be deemed as unacceptable toxicity.

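### Endoscopic toxicity is scored only at about week 12, so erythema, edema or stricture unchanged since before SBRT could be classed as SBRT toxicity under 12.9.2

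*Combined protocol and SAP*

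**What the plan says.** **Timing.** Section 10.5: "The endoscopic evaluation (including EUS) will take place at approximately 12 weeks post radiation". In the Study Calendar (section 5.0) the row "Endoscopy with duodenal evaluation, core biopsies if possible, cytologic brushings" is marked only in the 12-week column. The endoscopy before treatment has its own row, "Endoscopy with Fiducial placement for CT guided on-line positioning (not necessary for MR-linac treatments), core biopsies, cytologic brushings", which mentions no scoring.

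**Scale.** Section 10.5 gives four items 0 to 2 points each. A total of 0 means no toxicity, 1–2 mild, 3–4 moderate, and 5 or more severe. Neither a change from baseline nor an attribution step is described.

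**Use.** Section 12.9.2: "If endoscopy exhibits severe toxicity, the patient will be deemed as unacceptable toxicity". The synopsis (Assessment Criteria) defines unacceptable toxicity of SBRT as related grade 3 or 4 GI toxicity or death within 90 days.

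**Entry.** Section 6.1.1: "Patients must have no evidence of active duodenal or gastric ulcers or direct tumor invasion of the bowel or stomach on pre-SBRT endoscopy". Section 4.1 provides for duodenal stents: "Patient must have metal stent in place if duodenal stent is required". Section 4.2 adds: "Radiological infiltration into bowel is allowed, unless deemed clinically unsafe".

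**The concern.** A single absolute score at week 12 cannot separate radiation injury from what the tumor or a stent had already done to the bowel. The population makes this a practical matter, because patients with a duodenal stent or with radiological infiltration of the bowel may enter. The pre-SBRT endoscopy looks for ulcers and invasion and is not asked to grade the other three items. Section 10.5 has the endoscopist record where the tumor lies, but not where the erythema, edema or stricture lies, so the two sources cannot be separated afterwards.

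At stake is whether a patient classed as unacceptable toxicity under 12.9.2 was in fact harmed by SBRT. If severe scores also feed the dose-finding endpoint, which the protocol leaves unclear, the same misclassification would bear on the 0.15 toxicity limit in 12.6.

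**Working it through.** The plan states no figure on this point to reproduce. The check has four steps.

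**1. Can items that are not screened out reach the severe cut alone?** Inputs: four items scored 0–2 and a cut of 5 (10.5); active ulcers excluded (6.1.1).

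- All combinations: 3^4 = 81, maximum total 8.
- With ulcers = 0: 3^3 = 27 combinations, maximum 2 + 2 + 2 = 6.
- Of these 27, 1 scores none, 9 mild, 13 moderate and 4 severe. These are counts of score patterns, not probabilities.
- The 4 severe patterns (erythema, edema, stricture) are (1,2,2), (2,1,2), (2,2,1) and (2,2,2). Each needs at least two items at the top score.

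Example: stricture 2 + edema 2 + erythema 1 = 5, all unchanged since before SBRT. Sections 10.5 and 12.9.2, read literally, make this severe and therefore unacceptable toxicity. With stricture 2 + edema 1 = 3, the patient is labelled moderate toxicity.

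**2. Does another section supply the missing baseline?**

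| Section | What it provides | Tied to the endoscopic score? |
|---|---|---|
| 9.3 | Conditions starting before randomization are history; a rise in grade counts as an adverse event; GI toxicity gets a causality review | No. Without a pre-SBRT score, worsening on this scale cannot be shown |
| 12.1 | Toxicity must be related | No. The score is not mentioned |
| 12.4 | Grade 3 or 4 GI toxicity or death within 90 days | No. The score is not mentioned |
| 12.9.1 | Dose-finding inputs: time to Toxicity and day-90 efficacy | No. The score is not mentioned |
| 12.9.2 | A severe score is unacceptable toxicity | Yes, with no baseline or relatedness condition |

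**3. What size would matter, if the score did enter dose finding?** This step is conditional. Let p be the prior mean toxicity (0.02, 0.07, 0.10; Table 5 and 12.7). Let q be the share of patients whose pre-existing findings alone score 5 or more. The documents give no q, so the values below are assumptions, and q is taken as independent of true toxicity.

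Apparent toxicity = 1 − (1 − p)(1 − q).

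| Level | p | q = 0.02 | q = 0.05 | q = 0.10 | q at which apparent toxicity is 0.15 |
|---|---|---|---|---|---|
| 1 | 0.02 | 0.040 | 0.069 | 0.118 | 1 − 0.85/0.98 = 0.133 |
| 2 | 0.07 | 0.089 | 0.117 | 0.163 | 1 − 0.85/0.93 = 0.086 |
| 3 | 0.10 | 0.118 | 0.145 | 0.190 | 1 − 0.85/0.90 = 0.056 |

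The chance of at least one such patient among 24 is 1 − (1 − q)^24: 0.38, 0.71 and 0.92 at q = 0.02, 0.05 and 0.10.

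**4. Would subtracting the baseline score work?** Take the example patient, with baseline stricture 2, edema 2, erythema 1 and ulcers 0. The largest possible item-by-item change is 0 + 0 + 1 + 2 = 3. Against a cut of 5 this patient could never be called severe, even with two or more new ulcers. Subtraction would under-call injury in the patients whose bowel was most abnormal at entry.

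**The case against.** **The protocol already has a pre-existing-condition rule and a causality review (9.3), and 12.1 requires relatedness.** This shows what the authors intended. A reader might infer from 12.9.2 that pre-existing abnormalities will definitely be counted as SBRT toxicity. The documents do not go that far: it is the literal reading of one sentence, and 9.3 and 12.1 point the other way. But 9.3 governs adverse events, is not linked to this score, and could not be applied to it without a baseline value.

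**Dose finding is untouched.** A reader might also infer that the MTD is biased. Sections 12.1, 12.4 and 12.9.1 do not use the score, and the 12.9.2 sentence stands under secondary endpoints, just after a reference to descriptive statistics. The objection stands to this extent: an effect on dose selection is possible only if 12.9.2 is meant to feed the endpoint.

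**Arms are randomized and the endoscopist is blinded to drug.** Correct. Pre-existing abnormalities should balance between arms on average, so no systematic bias in the arm comparison follows. Randomization does not protect the absolute classification of a patient, or comparisons between adaptively assigned dose levels.

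**Small numbers prove nothing.** Also correct. One case among about 5 patients is 20 percentage points, but that holds for any event. Table 6 averages 10.1, 12.2 and 15.1 patients at the highlighted levels. Entry rules that exclude visible luminal invasion also make high baseline scores less likely. How a stented lumen would score for stricture is not stated.

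**A formal Statistical Analysis Plan may deal with this.** Section 12.9.1 defers analysis details to one. It could define the classification, but it cannot create baseline scores that were never recorded.

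**Conclusion.** The gap is real. The scale is applied only at about week 12, every point is labelled toxicity, and 12.9.2 attaches a consequence to a severe score without a baseline or relatedness condition. Three items that entry endoscopy does not screen out can total 6 against a cut of 5, so unchanged findings could be classed as SBRT toxicity.

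The size cannot be estimated, because the documents give no frequency of pre-existing findings. The values of q in the working are assumptions, and the comparison with 0.15 applies only if the score enters dose finding. The text does not support a stronger conclusion, either that the MTD is biased or that the arm comparison is. What it does support is a source of misclassification that is cheap to remove, and a conflict between 12.1 and 12.9.2 that must be settled.

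**What to change.** 1. In 10.5 and the Study Calendar, record the same four-item score at the pre-SBRT endoscopy that 6.1.1 already requires. The calendar note on MR-linac treatments should make clear that it waives the fiducials, not the baseline examination.
2. Report the absolute week-12 score alongside the item-level baseline.
3. In 12.9.2, count a week-12 score of 5 or more as SBRT toxicity only if at least one item is new or worse than baseline and judged related, in line with 9.3 and 12.1. In the worked example, an unchanged score of 5 would not count. The same patient with new ulcers judged related would.
4. Do not subtract scores against the same cut of 5, because of the ceiling shown above.
5. Reconcile 12.1 and 12.4 with 12.9.2 by stating whether a severe endoscopic score enters the dose-finding Toxicity endpoint.

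**Cost.** One CRF page and no new procedure where the 6.1.1 endoscopy is done. Patients already enrolled need baseline scores taken from existing endoscopy reports, or set to missing, and the plan should say in advance how patients with a missing baseline are classified.
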